Prior to July 2017, the only drug specifically approved for the treatment of SCD was hydroxyurea (HU), a small molecule inhibitor of ribonucleotide reductase that was originally developed for the treatment of myeloproliferative disorders. HU (also known as hydroxycarbamide) has been approved to treat SCD since 1998 in the United States (US) and since 2001 in Europe. In SCD, HU reduces painful crises and the need for blood transfusions (Charache 1995), at least in part by increasing levels of fetal hemoglobin (HbF), which reduces RBC sickling and improves blood flow. These effects are mediated, at least in part, by increased nitric oxide (NO) and cyclic guanosine monophosphate (cGMP) production (Erard 1981; Platt 1984; Cokic 2003). Unfortunately, HU is often poorly tolerated, and its widespread use is limited by concerns about its potential impact on fertility and reproduction, challenges achieving and maintaining an efficacious dose due to its hematologic toxicities, and requirements for monthly monitoring (Heaney and Ware 2008).

In July 2017, L-glutamine oral powder (EndariTM) was approved in the US to reduce complications of SCD. In November 2019, crizanlizumab (Adakveo[®]) and voxelotor (Oxbryta[®]) were approved by the Food and Drug Administration (FDA). Crizanlizumab (Adakveo[®]) is a humanized, anti-P-selectin monoclonal antibody that reduces the frequency of VOCs in adults and adolescents over the age of 16 years. Voxelotor (Oxbryta[®]) is an oral, once daily (qd) drug that binds to the α -chain of HbS, stabilizing the molecule in the R-state conformation, which is known to interrupt HbS polymerization. Both drugs are among the new therapies targeting

multiple pathways in the complex pathophysiology of SCD (Ballas 2020); however, due to the current cost of voxelotor (Oxbryta®) and crizanlizumab (Adakveo®), these therapies may not be accessible globally, especially for patients in resource-poor countries. Thus, additional accessible, novel, safe, and effective treatments to prevent the morbid complications of SCD in patients of all ages are still urgently needed.

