^d Vital signs include HR, respiratory rate, BP, and body temperature and should be consistently measured in either the sitting or semi-supine position. At the Day 1 and Week 4 visits, vital signs will be taken pre-dose and 2 hours (\pm 20 minutes) post-dose, during the PK assessments. At all other timepoints, vital signs can be taken irrespective of taking study drug.

^e Complete PEs will be performed at Screening and at Weeks 12, 24, 36, 52, and 56; these consist of a general examination of the body, including the abdomen, heart, lungs, lymph nodes, back/neck, neurological system, skin, extremities, head, eyes, nose, and throat. At all other visits, symptom-directed PEs will be obtained after identification of AEs deemed by the investigator to be of significant clinical concern.

^f All ECGs to be performed in triplicate. At the Baseline, Week 1, and Week 4 visits, ECGs will be obtained pre-dose and 2 hours (\pm 30 minutes) post-dose. At all other timepoints, ECG will be taken pre-dose.

^g Females of childbearing potential only. A serum pregnancy test will be performed during screening via a central laboratory. All subsequent pregnancy tests will be urine pregnancy tests performed locally (with test kits provided by the central laboratory). If a urine pregnancy test is positive, the result must be confirmed with a serum pregnancy test.

^h Serum virology (screening assessment) will be conducted only if clinically indicated. Testing will be performed through a central laboratory and may include HBsAg, hepatitis A IgM, and HCV antibody.

ⁱ AEs and concomitant medications, including opioids and HU use, will be recorded at each visit throughout the study from screening through the EOS (Week 56) follow-up.

^j Includes HbF and % F-cells. Blood samples should be obtained prior to administration of study drug.

^k PD biomarkers that are not already assessed as part of standard hematology or serum chemistry testing may include, but are not limited to, the following: soluble E-selectin, P-selectin, ICAM-1, VCAM-1, and MPO.

^l QoL assessments include the specified components of the ASCQ-Me[®], PROPr, SCSES. Refer to Section 11.2.4. The translated QoL assessments from PROPr will be used when available.

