8. SELECTION AND WITHDRAWAL OF SUBJECTS

8.1. Subject Inclusion Criteria

Each subject must meet all the following criteria to be enrolled in the study:

1. Male or female aged ≥ 18 to ≤ 65 years at the time of ICF signing.
2. Confirmed diagnosis of SCD (HbSS, HbS β^0 thalassemia, or HbS β^+ thalassemia) in the medical record; if not available, the diagnosis must be confirmed at the site's local laboratory instead.
3. Subjects must have had at least 2 and no more than 12 documented episodes of VOC in the past 12 months at the time of ICF signing and at randomization (Day 1).

For study eligibility, VOC is defined as a documented episode of an acute painful crisis (for which there was not an explanation other than VOC) that involved moderate to severe pain lasting for at least 2 hours and at least one of the following:

- Use of escalated analgesia (including healthcare professional-instructed use of an analgesic prescription)
- A hospital, emergency department, or clinic visit and/or healthcare telephone consultation at the time of occurrence
- Diagnosis of ACS (defined as an acute illness characterized by fever and/or respiratory symptoms, accompanied by a new pulmonary infiltrate on a chest X-ray), hepatic sequestration, splenic sequestration, or priapism (in males)

4. Hb of >5.5 and <10.5 g/dL; Hb values within 21 days post-transfusion will be excluded.
5. *This inclusion criterion has been removed.*
6. Subjects receiving HU must have received it continuously for at least 6 months prior to signing the ICF, and must have been on a stable dose for at least 3 months prior to signing the ICF, with no anticipated need for dose adjustments during the study including the screening period, in the opinion of the investigator.
7. Female subjects must not be pregnant or breastfeeding and be highly unlikely to become pregnant. Male subjects must be unlikely to impregnate a partner. Male or female subjects must meet at least one of the following criteria:

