Initially, subjects will be randomly assigned in a 2:1 ratio to receive either IMR-687 lower dose or placebo. Prior to the introduction of IMR-687 higher dose, the Data Monitoring Committee (DMC) will review safety data for at least 5 subjects who received IMR-687. If the DMC recommends inclusion of the higher dose, randomization will then proceed in a 1:2:1 ratio (IMR-687 lower dose, IMR-687 higher dose, or placebo). During study conduct under Protocol Version 3.0, the DMC approved opening of enrollment to the higher dose IMR-687 group, enrollment to the higher dose went into effect on 12 March 2021.

[figure not shown]
Subjects may or may not be concomitantly receiving a stable dose of hydroxyurea (HU) according to the subject's established treatment plan. Randomization will be stratified by use of HU (yes vs. no) and by region (North America/Europe vs. Africa/Middle East).

Subjects will be directed to take study drug (either IMR-687 or placebo) with food, but if a subject does not do so, it will not be considered a protocol deviation.

An interim analysis (IA) will be conducted when all subjects have completed study assessments (including VOC incidence) at Week 24 or terminated the study early. The IA will be a partial unblinding event with corresponding alpha spending strategies to manage Type 1 error.

A final analysis (FA) will be conducted at study completion (i.e., when all subjects have reached Week 56 or terminated early), following database lock and unblinding. Alpha available at the final analysis will be propagated based on the alpha spent from the IA.

Figure 1: Overview of Study Design and Dose Groups

Abbreviation: DMC = data monitoring committee.

* Prior to the introduction of IMR-687 higher dose, the DMC will review safety data for at least 5 subjects who received IMR-687. If the DMC recommends inclusion of the higher dose, randomization across 3 dose groups will then proceed as shown.

During study conduct under Protocol Version 3.0, the DMC approved the opening of enrollment in the higher dose IMR-687 group, which went into effect on 12 March 2021.

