13.5.3.2.1 Analysis and Imputation Methods

HbF responder rate (as defined by the proportion of subjects with an absolute increase of $\geq 3\%$ from baseline) at Week 24 will be assessed using a stratified Cochran-Mantel-Haenszel (CMH) test adjusted for stratification factors of region (North America/Europe vs. Africa/Middle East) and HU use (Yes vs. No). The ITT set will be used for this analysis.

The frequency and percentage of responders and non-responders at Week 24 will be presented for each treatment group as well as ORs, RRs, 95% Cis, and p-values from the CMH test comparing active groups to placebo.

Bar plots will be provided, and the proportion of subjects with response in HbF in each treatment group, Odds ratios, 95% CI, and p values will be displayed for each treatment comparison.

The following imputation rules will be applied for the key secondary efficacy endpoint (HbF responder at Week 24):

1. Subject will be treated as a non-responder if there is an initiation of HU post randomization and prior to Week 24.
2. If HbF value is missing at Week 24, the HbF value at Week 16 will be used for the analysis. If HbF value at Week 16 is also missing, subject will be treated as a non-responder.
3. Any HbF value within 8 weeks (56 days) of a RBC transfusion will be excluded from all analyses. If the subject does not have a valid HbF value at Week 24 and/or Week 16, subject will be treated as a non-responder.

Number of subjects with imputed values for the key secondary efficacy endpoint and the reason for imputation (imputed as non-responder because of initiation of HU post randomization, imputed with Week 16 value because of Week 24 value is missing, imputed from the last post-baseline assessment prior to RBC transfusion) will also be summarized. The observed and imputed Week 24 HbF values will both be summarized for the by-visit analysis.

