Annualized rate of days hospitalized for VOC-related hospitalization will be analyzed in the same way as annualized rate of VOC-related hospitalization.

Time to first for VOC-related hospitalization

The time to first VOC-related hospitalization event will be analyzed using Kaplan-Meier methods. Time in months to the first VOC-related hospitalization event can be calculated as ([date of first VOC-related hospitalization event – date of first dose + 1] / 30.4375).

Time to second VOC

This analysis of time to second VOC event will be analyzed using Kaplan-Meier methods similar to the analysis of the time to first VOC. A patient with less than two VOCs before withdrawal or completion of the study is considered censored at the time of withdrawal or completion of the study.

A sensitivity analysis will be performed separately, excluding these subjects without any VOCs.

HbF responder rate (as defined by proportion of subjects with an absolute increase of $\geq 3\%$ in HbF from baseline) at Week 52

This analysis of HbF responder at Week 52 will be similar to the HbF responder rate analysis at Week 24 ([Section 13.5.3.2](#)). Similar imputation rules will apply:

1. Subject will be treated as a non-responder if there is an initiation of HU post randomization and prior to Week 52.
2. HbF value from Week 36 (the last scheduled visit before the target analysis visit) will be used when Week 52 value is missing,
3. Any HbF value within 8 weeks (56 days) of RBC transfusion is excluded from all analyses.

Change from baseline in HbF (%) and F-cells (%) at Week 24 and Week 52

Change and percentage change from baseline in HbF (%) and F-cells (%) will be analyzed using mixed models for repeated measures (MMRM) with baseline value as a covariate, fixed effects for region (North America/Europe vs. Africa/Middle East), HU use (yes vs. no), treatment, visit, and treatment-by-visit interaction. Unstructured covariance matrices will be assumed for all models, but auto-regressive 1 (AR1) and compound symmetry (CS) may also be assessed (in that order) if the unstructured covariance matrix does not converge.

Values used at the visit and change from baseline for each parameter will be summarized for each post-baseline timepoint. The LS Mean estimates and 95% CIs will be displayed for all treatment groups. LS Mean difference estimates and 95% CIs with p-values for all IMR-687 treatment groups (relative to placebo) will be provided.

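### The HbF and Hb responder rules count only starting HU as non-response, so a subject already on HU whose dose is raised can still be scored a responder

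*SAP*

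**What the plan says.** **The responder rule.** For HbF response at Week 24 (SAP 13.5.3.2.1), the first of three imputation rules is: "Subject will be treated as a non-responder if there is an initiation of HU post randomization and prior to Week 24". The other two deal with missing values and RBC transfusion. The imputation reasons to be tabulated for HU also name only initiation.

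**Where it recurs.** For Week 52, SAP 13.5.4 states: "Subject will be treated as a non-responder if there is an initiation of HU post randomization and prior to Week 52". The same section applies these rules to Hb response at Weeks 24 and 52.

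**Background HU.** SAP 8.0 describes the population: "Subjects may or may not be concomitantly receiving a stable dose of hydroxyurea (HU) according to the subject's established treatment plan". Under Protocol 8.1, inclusion criterion 6, HU users need 6 months of uninterrupted use and 3 months at an unchanged dose before consent. The criterion then adds a forward-looking condition: "with no anticipated need for dose adjustments during the study including the screening period, in the opinion of the investigator". Protocol 9.6 repeats this. Protocol 9.6.2 does not list a change of HU dose among the prohibited therapies, and the deviation categories in SAP 13.2 do not name one.

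**Data available.** A footnote to the schedule of assessments (Protocol Table 1) says: "AEs and concomitant medications, including opioids and HU use, will be recorded at each visit throughout the study". Protocol 9.6 requires dose, frequency and dates for every concomitant medication.

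**The concern.** The first rule exists because HU itself raises HbF, as Protocol 4.1 says, and the sponsor does not want such a rise credited to IMR-687. Initiation can in practice occur only among subjects not on HU at entry. For those already on HU, the corresponding event is a dose increase, and the rule is silent on it. One confounder is therefore neutralised in one randomization stratum and left open in the other.

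HbF response at Week 24 is the second key secondary endpoint and step 3 of the fixed sequence, so every later step depends on it. An HU-driven responder on placebo hides a drug effect; one on active treatment adds to the apparent effect. With few placebo responders expected, single subjects carry weight.

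**Working it through.** **Does anything else in the plan close the gap?**
- Inclusion criterion 6 records the investigator's expectation at entry. It is not an on-study restriction.
- The sensitivity analyses in SAP 13.5.3.2.2 vary only the use of Week 12, 16 and 24 values and repeat the analysis in the mITT and PP sets. All run at the final analysis only.
- The PP definition (SAP 11.6) could remove such a subject if the sponsor, while blinded, classes the increase as a major deviation or an event affecting the analysis. That is not prespecified for HU.

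So the event is identifiable from recorded data, but no analysis rule addresses it.

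**The plan's own figure.** SAP 8.1.1 gives 31 placebo and 49 higher-dose subjects, 5% against 35%, a continuity-corrected chi-square test at two-sided 0.05, and power above 85%.
- Pooled rate: (31 × 0.05 + 49 × 0.35)/80 = 18.7/80 = 0.2338
- SE under the null: √[0.2338 × 0.7662 × (1/31 + 1/49)] = 0.0971
- SE under the alternative: √[0.05 × 0.95/31 + 0.35 × 0.65/49] = 0.0786
- Continuity correction: 0.5 × (1/31 + 1/49) = 0.0263
- z = (0.30 − 0.0263 − 1.96 × 0.0971)/0.0786 = 1.06, so power is 85.5% (87.4% by exact enumeration)

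The stated figure is reproduced.

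**Weight of one subject.**
- Placebo: 31 × 0.05 = 1.55 responders expected; one more adds 1/31 = 3.2 points.
- Higher dose: 49 × 0.35 = 17.15 expected; one more adds 1/49 = 2.0 points.

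**How many subjects might be affected?** The documents give neither input. Assume 50% on HU and 2% to 10% of those escalating before Week 24.
- Placebo: 31 × 0.5 = 15.5 on HU; × 0.02 to 0.10 = 0.3 to 1.6 escalated
- Higher dose: 49 × 0.5 = 24.5 on HU; × 0.02 to 0.10 = 0.5 to 2.5 escalated

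If 35% to 50% of escalated subjects reach +3 points because of HU (also assumed), placebo gains at most 0.31 × 0.35 = 0.1 to 1.55 × 0.50 = 0.8 responders.

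**Effect on power at the top of that range.** Escalated subjects are 0.5 × 0.10 = 5% of each arm, and 0.05 × 0.50 = 2.5% of each arm reach +3 points through HU.

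| Case | Placebo | Higher dose | Power |
|---|---|---|---|
| As planned | 5% | 35% | 85.5% |
| Rule as written, escalation in both arms | 5% + 2.5% × 0.95 = 7.4% | 35% + 2.5% × 0.65 = 36.6% | 80.2% |
| Rule as written, escalation on placebo only | 7.4% | 35% | 75.5% |
| Escalated subjects set to non-response in both arms | 5% × 0.95 = 4.75% | 35% × 0.95 = 33.25% | 82.3% |

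A full extra responder in the placebo expectation (5% + 3.2 = 8.2%, higher dose held at 35%) would lower power to about 71%, but that lies above the assumed range. All these figures use the SAP's unstratified planning test, not the stratified CMH test.

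**The case against.** The strongest reply is that this is a choice of estimand. Counting the observed HbF despite a change in background dose is a legitimate treatment-policy approach, and starting a new HbF-raising drug need not be treated like adjusting an existing one. That would be persuasive had the plan taken the treatment-policy approach throughout. It did not: it already scores HU initiation as non-response, and gives no reason to treat an increase differently.

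Several other objections stand in part:
- A reader might infer that nothing holds the HU dose after randomization. The documents do not support that. The no-anticipated-adjustment condition covers the study period and selects subjects in whom escalation is not expected.
- A reader might infer that the placebo rate would more than double. That needs two HU-driven placebo responders, more than the 1.6 escalated placebo subjects at the top of the assumed range.
- Baseline HbF already includes the effect of the existing HU dose (SAP 10.2). The documents do not say how often an increase would add 3 points by Week 24.
- The CMH test is stratified by HU use, and SAP 13.5.6 plans subgroup analyses by baseline HU use. An anomaly in the HU = Yes stratum might be seen, but its cause would not be separated from a drug effect.
- A rule on increases ignores reductions. Its purpose, though, is to stop HU-driven responses being credited to IMR-687, and a reduction would not be expected to create one.

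**Conclusion.** The gap is real and modest. As written, a HU = Yes subject whose dose is raised and whose HbF is at least 3 points above baseline at Week 24 is a responder. The same holds at Week 52, and for Hb response with its own threshold. Entry selection lowers the chance of this without removing it.

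The size rests on assumed inputs: about 0.3 to 1.6 escalated placebo subjects and 0.5 to 2.5 on the higher dose, with fewer misclassified responders. The direction is unknown, since more increases on placebo would dilute the effect and more on active treatment would inflate it. Power is not the main argument: in the two-arm example the extended rule gives 82.3% against 80.2%. The argument is that a responder should mean the same thing in both HU strata.

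A reader might infer that the primary result is at risk. It is not: the annualized VOC rate does not use this rule. HbF response is formally tested only if that endpoint and time to first VOC both succeed. Nor does the defect call for removing post-increase values from the MMRM, which the present rule does not do even after initiation, or for censoring VOCs at an HU change, which could itself be informative.

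**What to change.** Before unblinding, reword the first rule in SAP 13.5.3.2.1, and the matching Week 52 and Hb rules, so that non-response follows *initiation of HU, or an increase in HU dose above the baseline dose, after randomization and before the analysis visit*. Add this category to the tabulated imputation reasons, report the number of such subjects by arm, and keep the initiation-only rule as a sensitivity analysis.

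No new data are needed: the flag comes from HU dose and dates already recorded, and occurrences can be counted while the data are blinded. If there are none, the results are unchanged.

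The downside is that a few true responders with an HU increase become non-responders. If increases are commoner on placebo, the extended rule may slightly favour the drug, which the sensitivity analysis would show. This changes the analysis only; no HU dosing rule is proposed.

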8.5. Guidelines for Study Drug Dose Withholding or Discontinuation

In consultation with the medical monitor, the investigator may decide to withhold or discontinue study drug dosing in cases where tolerability or safety concerns emerge. [Table 2](#) provides recommended guidelines for these decisions.

If a study drug dosing is withheld due to an AE (Section [12](#)), subjects who continue on the study will have all assessments (except study drug administration) performed as per protocol.

If study drug dosing is discontinued for any reason, the specific circumstances surrounding the discontinuation must be recorded in the subject's eCRF. Any subject who discontinues study drug dosing must also be withdrawn from the study; however, all appropriate safety assessments and follow-up should be completed prior to withdrawal (Section [8.4](#)).

Table 2: Safety Guidelines for Study Drug Dose Reduction, Withholding, or Discontinuation

Dose Reduction	
Event	Recommended Action
A Grade 2 or higher TEAE that, in the opinion of the investigator, is both study drug related and that makes continued dosing at the current dose level inadvisable due to safety concern or lack of tolerability.	
Study drug may be reduced by 1 tablet for up to 14 continuous days.
 
If, in the opinion of the investigator, a longer dose reduction is clinically needed, the medical monitor should be contacted.
 
If, in the opinion of the investigator, the severity of the Grade ≥ 2 TEAE has reduced to Grade ≤ 1, the subject may resume study drug at the original dose. If the TEAE recurs after re-introduction of the original dose, the subject should be withdrawn from the study.

Dose Interruption (Hold)	
Event	Recommended Action
A Grade 3 or higher TEAE that, in the opinion of the investigator, is both study drug related and that makes continued dosing at the current dose level inadvisable due to safety concern or lack of tolerability.	
Study drug should be held for up to 7 continuous days until reduction in severity of the TEAE to Grade ≤ 2, then resumed at the original dose.
 
If, in the opinion of the investigator, dosing should be resumed at a lower dose, the medical monitor should be contacted.
 
If, in the opinion of the investigator, a longer dose hold is clinically needed, the medical monitor should be contacted or the subject should be withdrawn from the study.

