8.1 Sample Size and Power Considerations

8.1.1 Sample Size Determination

The sample size of this study was originally determined based on HbF responder rate as the primary endpoint:

Assuming a 5% HbF response rate for placebo, the study having approximately 31 placebo and 49 higher dose subjects would have > 85% power to detect a targeted difference of 30%, using a Chi-square test for comparison of proportions (with continuity-correction) and a two-sided alpha of 0.050. The assumed responder rate for placebo (5%) and highest tolerated dose subjects (>35%) includes the dropout subjects (regarded as are non-responders at Week 24).

Based on FDA feedback a new primary endpoint was adopted with a corresponding change in statistical methodology as specified in Section 8.1.2 below.

As of completion of this SAP, enrollment was completed in the ongoing study, with a total of 115 subjects randomized between August 2020 and August 2021. Out of the 115 subjects, the first 17 subjects were randomized in a 2:1 ratio to Lower Dose: Placebo, and the remaining 98 subjects proceeded with randomization in a 1:2:1 ratio for Lower Dose: Higher Dose: Placebo.

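### A subject who stops study drug before Week 24 can count as a Week 24 HbF responder in the main analysis, although SAP 8.1.1 sizes that comparison with dropouts as non-responders

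*SAP*

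**What the plan says.** **Sizing.** SAP 8.1.1 states: "Assuming a 5% HbF response rate for placebo, the study having approximately 31 placebo and 49 higher dose subjects would have > 85% power". The effect sought is 30 percentage points, and the comparison is made "using a Chi-square test for comparison of proportions (with continuity-correction) and a two-sided alpha of 0.050". The section adds that the assumed rates, 5% on placebo and above 35% on the highest tolerated dose, "includes the dropout subjects (regarded as are non-responders at Week 24".

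**Analysis.** SAP 13.5.3.2.1 analyses the Week 24 responder rate in the ITT set. Rule 2 reads "If HbF value is missing at Week 24, the HbF value at Week 16 will be used for the analysis", followed by "If HbF value at Week 16 is also missing, subject will be treated as a non-responder". No condition is placed on why the Week 24 value is missing. Rules 1 and 3 deal with hydroxyurea started after randomization and with values near a transfusion; neither deals with stopping study drug.

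**Discontinuation.** Protocol 8.5 says "Any subject who discontinues study drug dosing must also be withdrawn from the study".

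**Windows.** SAP 10.5, Table 2, puts Days 100–141 in the Week 16 window and Days 142–211 in the Week 24 window. The early discontinuation visit may fill either.

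**Strict version.** SAP 13.5.3.2.2 lists, as sensitivity analysis 2, non-response for anyone without a Week 24 value. All the sensitivity analyses there are run at the final analysis. The endpoint stands third in the testing order at both the interim and the final analysis (SAP 12.3 and 12.4).

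**Related endpoints.** For Week 52, SAP 13.5.4 says "HbF value from Week 36 (the last scheduled visit before the target analysis visit) will be used when Week 52 value is missing". The Hb responder endpoints take over the same rules, and the imputed HbF values also enter the MMRM.

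**The concern.** The sizing statement and the main analysis treat the same subject differently. Someone who stops drug after a Week 16 sample is a failure in SAP 8.1.1 and can be a success under rule 2, despite having been off drug for weeks by Week 24. The window rule opens a second route: an early termination sample on, say, Day 150 is simply the Week 24 value.

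At stake is what the Week 24 responder rate means. Read as SAP 8.1.1 has it, it is the share of randomized subjects who stay in the study and respond. As analysed, it also includes some subjects who responded and then left. If response is much more common on drug than on placebo, these additions fall mainly in the IMR-687 arms. A claim on this endpoint at the interim analysis would come without the strict check.

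**Working it through.** **1. The plan's own figure.** Inputs from SAP 8.1.1: n = 31 and 49, rates 5% and 35%, continuity-corrected chi-square test, two-sided 0.05.

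- Pooled rate = (31 × 0.05 + 49 × 0.35)/80 = 0.234
- Standard error under the null = √[0.234 × 0.766 × (1/31 + 1/49)] = 0.0971
- Standard error under the alternative = √(0.05 × 0.95/31 + 0.35 × 0.65/49) = 0.0786
- Continuity correction = 0.5 × (1/31 + 1/49) = 0.0263
- Power = Φ[(0.30 − 0.0263 − 1.96 × 0.0971)/0.0786] = Φ(1.06) = 85.5%

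Exact enumeration gives 87.4%. The stated figure of more than 85% reproduces, with dropouts counted as non-responders.

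**2. Which leavers are affected** (SAP Table 2 windows)

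| Leaves | HbF available | Status in the main analysis |
|---|---|---|
| Before about Day 100 | none in the Week 16 window | non-responder, as in 8.1.1 |
| Days 100–141, early termination sample taken | Week 16 window | Week 16 value used by rule 2 |
| After the Day 112 visit, no early termination sample | scheduled Week 16 value | Week 16 value used by rule 2 |
| Day 142 to before Week 24, early termination sample taken | Week 24 window | observed Week 24 value; rule 2 not used |

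**3. How many rule 2 reaches.** Protocol 13.7 gives 20% dropout before Week 24 (Day 168). The documents do not give its timing, so I assume it is evenly spread and equal across arms.

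- Early termination samples taken: 42/168 × 20% = 5.0%
- None taken: 56/168 × 20% = 6.7%

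**4. Effect on the difference**, if leavers respond like the rest of their arm.

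- At 35% v 5%: 0.050 × 30 = 1.5 points; 0.067 × 30 = 2.0 points
- Those rates already count dropouts as failures. The implied completer rates are 0.35/0.80 = 43.75% and 0.05/0.80 = 6.25%, a gap of 37.5 points. Then 0.050 × 37.5 = 1.9 points; 0.067 × 37.5 = 2.5 points
- Extra higher-dose responders: from 49 × 0.050 × 0.35 = 0.9 to 49 × 0.067 × 0.4375 = 1.4
- Extra placebo responders: at most 31 × 0.067 × 0.0625 = 0.1

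**5. The window route.** Where early termination samples are taken, leavers on Days 142–160 add 19/168 × 20% = 2.3% of subjects: 0.023 × 30 = 0.7 points, or 0.8 with completer rates.

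**6. Sensitivity to the unknown timing.** With dropout of 10% to 25%, and 25% to 100% of dropouts having a Week 16 value, rule 2 makes the 30-point difference 30.8 to 40.0 points. The top of that range needs 25% dropout with every dropout having a Week 16 value. Nominal power rises from 85.5% to between 87.2% and 97.5%.

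**The case against.** The other side has several sound points.

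- **The sizing sentence is historical.** It dates from when HbF response was the primary endpoint. Current power (SAP 8.1.2) is for the VOC rate. Protocol 13.7 uses yet another basis: 26 per arm remaining at Week 24, and 26/0.80 = 33 per arm, 99 in all. This stands: no current design figure fails. But the sentence is still in the SAP and still contradicts rule 2.
- **The strict analysis is prespecified.** True. The question is which analysis is the main one. Sensitivity analysis 2 also leaves the window route open, because an early termination value from Day 142 is not missing.
- **The interim gap is rarely reached.** HbF response is tested there only if the VOC rate passes at 0.002 and time to first VOC also succeeds. This limits the gap without closing it.

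A reader might also infer more than the documents support:

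- *That the rule inflates type I error.* The widening is computed with the drug already working. With equal response and equal dropout, both arms gain equally.
- *That discontinuation is hidden.* SAP 13.5.3.2.1 reports how many values are imputed and why, and SAP 13.1 tabulates discontinuations with reasons.
- *That most missing Week 24 values come from dropouts.* No document gives the split. Missed samples and values excluded after transfusion also contribute, and Protocol 9.6.3 lets transfused subjects stay in.
- *That Week 52 HbF and Hb response depart from their power basis.* No power is stated for them.

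**Conclusion.** The inconsistency is real, and small. In the main analysis of key secondary endpoint 2, a subject who stopped drug before Week 24 can count as a responder, by rule 2 or by the visit windows, whereas SAP 8.1.1 counts that subject as a non-responder. Rule 2 alone reaches about 5.0% to 6.7% of subjects and widens the observed difference by 1.5 to 2.0 points, or 1.9 to 2.5 with completer rates: about one higher-dose responder, against a targeted 30 points.

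This rests on 20% dropout, evenly spread and equal across arms, and on leavers responding like others in their arm. It also requires a working drug. It is a mismatch in what is estimated. It is neither an arithmetic error nor a demonstrated false-positive risk, and it does not touch the VOC primary endpoint.

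**What to change.** Replace rule 2 with wording such as: *A subject who discontinued study drug before the scheduled Week 24 visit window opens (Day 168 − 7 = Day 161) is a non-responder, including when an early termination value falls in Days 142–211. The Week 16 value is used only for a subject still on study drug whose Week 24 value is missing or invalid.*

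Apply it at both the interim and final analyses, and keep the present carry-forward as a sensitivity analysis. The explicit day is needed because the analysis window opens at Day 142, before the scheduled visit window.

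For consistency, use the parallel rule for Week 52 HbF, where the value now carried forward is 16 weeks old, and for the Hb responder endpoints. State which HbF values of discontinued subjects enter the MMRM.

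If the sponsor keeps the present rule as the main analysis, correct the dropout sentence in SAP 8.1.1 and run sensitivity analysis 2 at the interim as well.

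The cost is SAP wording and a slightly lower reported responder rate. No new data or sample size are needed: stated power stays at 85.5%, because it is already defined on the strict basis. If the 5% and 35% were in fact meant as rates after carry-forward, strict counting at 20% dropout would give 81.7% power with a quarter of dropouts having a Week 16 value and 77.7% with half. The sponsor should therefore confirm which was meant.
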